Efficacy Endpoints	
Note that a pre-treatment value for Hb and RBC count is defined as the average of 2 values obtained prior to treatment, ie, the qualifying screening value and the baseline value. Last observation before the first dose of study medication will be used as baseline for other parameters.
 
Primary Endpoint:
 

Mean change in Hb levels from pre-treatment to the end of the primary efficacy period (Week 6)

 
Secondary Endpoints:
 

Proportion of subjects who achieve target Hb 10-12 g/dL at the end of the open-label extension period (Week 16)

Mean change in Hb between pre-treatment and the end of the open-label extension period (Week 16)

Mean change in hematocrit, RBC count, and reticulocyte count from pre-treatment to the end of the primary efficacy period (Week 6) and the end of the open-label extension period (Week 16)

Mean change in iron indices (ie, iron, total iron-binding capacity [TIBC], TSAT, and ferritin) and hepcidin from pre-treatment to the end of the primary efficacy period (Week 6) and the end of the open-label extension period (Week 16)

Proportion of subjects with confirmed Hb values <10.0 or >12.0 g/dL from pre-treatment to the end of the open-label extension period (Week 16)

Proportion of subjects requiring rescue with RBC transfusion from baseline to the end of the primary efficacy period (Week 6) and the end of the open-label extension period (Week 16)

Proportion of subjects requiring rescue with ESAs from baseline to the end of the primary efficacy period (Week 6) and the end of the open-label extension period (Week 16)

Number of dose adjustments from baseline to the end of the primary efficacy period (Week 6) and the end of the open-label extension period (Week 16)

Maintenance of iron sufficiency (defined as ferritin <math>\geq</math>50 ng/mL and TSAT <math>\geq</math>20%) from baseline to the end of the primary efficacy period (Week 6) and the end of the open-label extension period (Week 16)

Plasma concentration profile of vadadustat and its metabolites using pre-dose sample from Week 4

Safety Endpoints	Safety and tolerability assessments, including adverse events, vital signs, electrocardiograms (ECGs), and other laboratory assay results (eg, chemistry,

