Statistical Considerations	
The primary analysis will use a linear regression analysis to quantify the association between vadadustat dose and mean change in Hb (ie, to assess the vadadustat dose-response relationship). Comparison of each vadadustat dose group versus baseline will be performed. All tests of significance will be performed using a 0.05 two-sided significance level.
 
The target enrollment will be approximately 48 subjects for the study with 12 subjects enrolled in each of the 4 treatment groups. Based on the results from Study AKB-6548-CI-0005 that was conducted in the United States and evaluated vadadustat in patients with anemia secondary to NDD-CKD, the expected mean Hb changes from baseline to Week 6 will be 0, 0.5, 0.7, and 1.2 g/dL for the placebo, 150 mg, 300 mg, and 600 mg vadadustat dose groups, respectively, with a common standard deviation of 0.68 g/dL among the 4 treatment groups. With these assumptions, the study will have >85% power to detect a non-zero slope in a dose-response relationship using linear regression analysis and <math>\alpha=0.05</math>, based on simulation of 10,000 repetitions using SAS® software, Version Number 9.4.

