### 5.2 Secondary Objectives and Endpoints

The secondary objectives of this study are:

- To assess the safety, tolerability, pharmacokinetics (PK), and pharmacodynamics (PD) of oral vadadustat once daily dosing in Japanese subjects with anemia secondary to NDD-CKD during the 6-week, primary efficacy period

- To evaluate the effect of dose adjustments and demonstrate the maintenance effect on Hb during a 10-week maintenance period

The efficacy endpoints that will be used to assess these objectives include the following:

- Proportion of subjects who achieve target Hb 10-12 g/dL at the end of the open-label extension period (Week 16)
- Mean change in Hb between pre-treatment and the end of the open-label extension period (Week 16)
- Mean change in hematocrit, RBC count, and reticulocyte count from pre-treatment to the end of the primary efficacy period (Week 6) and the end of the open-label extension period (Week 16)
- Mean change in iron indices (ie, iron, total iron-binding capacity [TIBC], TSAT, and ferritin) and hepcidin from pre-treatment to the end of the primary efficacy period (Week 6) and the end of the open-label extension period (Week 16)
- Proportion of subjects with confirmed Hb values <10.0 or >12.0 g/dL from pre-treatment to the end of the open-label extension period (Week 16)
- Proportion of subjects requiring rescue with RBC transfusion from baseline to the end of the primary efficacy period (Week 6) and the end of the open-label extension period (Week 16)
- Proportion of subjects requiring rescue with ESAs from baseline to the end of the primary efficacy period (Week 6) and the end of the open-label extension period (Week 16)
- Number of dose adjustments from baseline to the end of the primary efficacy period (Week 6) and the end of the open-label extension period (Week 16)
- Maintenance of iron sufficiency (defined as ferritin  $\geq$ 50 ng/mL and TSAT  $\geq$ 20%) from baseline to the end of the primary efficacy period (Week 6) and the end of the open-label extension period (Week 16)
- Plasma concentration profile of vadadustat and its metabolites using pre-dose sample from Week 4

The safety endpoints that will be used to assess these objectives include the following:

- Safety assessments, including adverse events, vital signs, electrocardiograms (ECGs), and other laboratory assay results (eg, chemistry, components of the complete blood count [CBC] other than the ones noted above, and vascular endothelial growth factor [VEGF])

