### 7.2 Inclusion Criteria

Subjects must meet all of the following inclusion criteria to be eligible for study participation:

1. Male and female Japanese subjects, aged 20 years or older
2. Diagnosis of CKD based on an estimated glomerular filtration rate (eGFR) of  $\leq 60$  mL/min/1.73 m^2 (using the 2009 Japanese Society of Nephrology equation; [Matsuo 2009](#))
3. Not currently being treated with dialysis and not expected to start dialysis within 3 months of screening
4. Hemoglobin (Hb)  $\leq 10.5$  g/dL during screening
5. Serum ferritin  $\geq 50$  ng/mL during screening
6. TSAT  $\geq 20\%$  during screening
7. Folate and vitamin B12 greater than or equal to the lower limit of normal during screening
8. Understands the procedures and requirements of the study and provides written informed consent and authorization for protected health information disclosure

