## 7.6 Subject Completion and Individual Subject Discontinuation

### 7.6.1 Subject Completion

A subject randomized to receive placebo will be considered as having completed the study after completing participation in the Week 10 (unblinding) visit.

A subject randomized to receive vadadustat will be considered as having completed the study after completing participation in the Week 18 visit (end of the 2-week safety follow-up period).

Note that for subjects who discontinue study drug due to an excess Hb response during the primary efficacy period, Hb levels will be monitored weekly via lab evaluation until the subject no longer exhibits an excess Hb response.

See [Section 10.3.6](#) for information regarding follow-up of unresolved events.

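### The Hb excursion endpoint opens its window before the first dose, in subjects who must enter at 10.5 g/dL or below, so entry anaemia is counted as an excursion and heavily dilutes any treatment signal

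*Protocol*

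**What the plan says.** The endpoint in Section 5.2 is the "Proportion of subjects with confirmed Hb values <10.0 or >12.0 g/dL from pre-treatment to the end of the open-label extension period (Week 16"). It reads the same in all three protocol versions in the file.

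The start of that window is defined in the synopsis: "Note that a pre-treatment value for Hb and RBC count is defined as the average of 2 values obtained prior to treatment", namely the qualifying screening value and the baseline value. The note that opens Section 5 says the same for Hb. Both values precede the first dose.

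Inclusion criterion 4 (Section 7.2) caps Hb at 10.5 "g/dL during screening" and sets no lower limit.

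Neighbouring event-type endpoints in Section 5.2 (rescue, dose adjustments, iron sufficiency) start at baseline and also have a Week 6 cut, for example "Number of dose adjustments from baseline to the end of the primary efficacy period (Week 6"). Elsewhere in the list the pre-treatment start is used for mean changes, where it is the natural reference.

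For placebo, Section 7.6.1 says: "A subject randomized to receive placebo will be considered as having completed the study after completing participation in the Week 10 (unblinding) visit".

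**The concern.** A mean change needs a pre-treatment reference. An event window should not include it, least of all when the entry criterion selects subjects in or near one of the event ranges. Taken literally, the endpoint scores the condition that qualified the subject for the trial as an excursion, in every arm alike.

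The endpoint serves the secondary objective on dose adjustment and maintenance of Hb. If much of each arm qualifies at entry, the reported proportion mainly describes whom the sites recruited. A subject who starts at 9.5 and is then held within 10-12 g/dL to Week 16 may be counted the same as one who never responds. Joining the two limbs adds a second loss: a proportion of, say, 70% does not show whether subjects stayed low or overshot.

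**Working it through.** **1. The plan's own figure.** No figure is stated for this endpoint; the only one is the power of more than 85% for the primary slope test. Inputs from the synopsis: "the expected mean Hb changes from baseline to Week 6 will be 0, 0.5, 0.7, and 1.2 g/dL", a common "standard deviation of 0.68 g/dL among the 4 treatment groups", 12 "subjects enrolled in each of the 4 treatment groups", two-sided 0.05. With doses 0, 150, 300 and 600 mg (mean 262.5), Sxx = 12 × (262.5² + 112.5² + 37.5² + 337.5²) = 2,362,500. The expected slope is 0.00190 g/dL per mg and its standard error is 0.68/√2,362,500 = 0.00044, a ratio of about 4.3. Simulation (20,000 repetitions) gives 98.7% power. The stated bound holds, and nothing below touches it.

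**2. Share already below 10.0 at entry.** The protocol gives no entry Hb distribution, so these are assumptions.

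- *Set A*: true Hb mean 10-11 and SD 0.8-1.0, within-subject SD 0.3-0.5, screening value of 10.5 or less with one retest, then a baseline draw (12 scenarios). Average of the two values below 10.0: 34-68%. Both values below 10.0: 21-59%, above half in 3 of 12 scenarios.
- *Set B*: entry Hb normal, truncated at 10.5. The share is Φ((10.0 − m)/s) / Φ((10.5 − m)/s). For m = 9.8, s = 0.6 this is Φ(0.33)/Φ(1.17) = 0.63/0.88 = 0.72. Over m = 9.0-10.3 and s = 0.4-1.0 it runs from 33% to 99%, above half in 22 of 24 scenarios.

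**3. Why this dilutes.** If a share f of every arm qualifies on pre-treatment values alone, and q is the event rate among the rest, the arm's proportion is f + (1 − f)q. A difference between arms is multiplied by (1 − f). With f = 0.21-0.59 the largest possible difference is 79 down to 41 points, and the actual one is smaller.

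**4. Effect on the endpoint, followed to Week 6.** Protocol effects and SD of change. Assumed: linear rise, within-visit SD 0.3 (so between-subject SD of change √(0.68² − 1.5 × 0.3²) = 0.57), confirmed = two consecutive values, no dose reductions, and three Set B entry distributions.

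| Entry (m, s) | Both pre-treatment values <10.0 | Counted window | Placebo | 150 mg | 600 mg |
|---|---|---|---|---|---|
| 9.3, 0.8 | 82% | as written | 90% | 86% | 84% |
| | | post-dose only | 85% | 77% | 65% |
| | | <10.0 at Weeks 4 and 6 | 75% | 58% | 31% |
| 9.8, 0.6 | 63% | as written | 78% | 72% | 67% |
| | | post-dose only | 71% | 57% | 40% |
| | | <10.0 at Weeks 4 and 6 | 57% | 35% | 12% |
| 10.0, 0.4 | 44% | as written | 67% | 56% | 50% |
| | | post-dose only | 57% | 39% | 21% |
| | | <10.0 at Weeks 4 and 6 | 43% | 21% | 4% |

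Check against step 3 for the middle case: f = 0.63, so the placebo remainder is (0.78 − 0.63)/0.37 = 0.41 and the 600 mg remainder is (0.67 − 0.63)/0.37 = 0.11. The difference is 0.37 × 0.30 = 0.11, as tabulated.

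The 150 versus 600 mg gap is 2-6 points as written, 12-18 when only post-dose values count, and 17-27 when the lower limb is read at Weeks 4 and 6. As a yardstick only, since no such test is planned, power for 600 mg against placebo at 12 per group is 6-13%, 20-43% and 58-66% respectively.

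**5. The upper limb.** Confirmed Hb above 12.0 by Week 6 occurs in at most about 1% of the 600 mg group in these runs.

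**The case against.** The strongest reply is that much of this belongs to the SAP. Section 11.5 of the two earlier protocol versions in the file leaves the full set of efficacy outcomes to it. The meaning of confirmed, and whether the limbs are tabulated in one row or two, could be settled there. That stands for the meaning of confirmed: Hb is measured by both the central laboratory and a point-of-care device, so agreement of the two, or of consecutive visits, could serve. It does not stand for the window. The protocol itself fixes the thresholds, their joining and the starting point, and an SAP that followed it would inherit the problem.

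A second reply is that dose separation is the task of the primary slope analysis, and that target attainment at Week 16, mean Hb change and number of dose adjustments already cover maintenance. That limits the consequence. It does not make this endpoint informative.

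A reader might infer more than the documents support:

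- *That most subjects meet the endpoint at entry.* Possible but not shown. Subjects entering at 10.0-10.5 do not meet it, and under Set A both pre-treatment values fall below 10.0 in only 21-59%.
- *That the endpoint cannot separate doses at all.* Subjects entering at 10.0-10.5, and the upper limb, still carry some information.
- *That a rise in values above 12.0 cancels the fall in values below 10.0.* The upper limb is too rare by Week 6 for that. The case for splitting the limbs is interpretability.
- *That the shorter placebo follow-up biases a planned comparison.* No placebo comparison on this endpoint is specified.

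**Conclusion.** The point holds as a defect in the stated wording of one of ten secondary efficacy endpoints. Because the window opens before the first dose and entry is capped at 10.5 g/dL with no floor, a large share of every arm, possibly most, can meet the lower limb at entry. The endpoint is then heavily diluted by entry status and can hardly reflect treatment, dose adjustment or maintenance. In simulation the contrast between 150 mg and 600 mg shrinks to 2-6 points.

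The direction follows from the text alone; the size rests on assumed entry distributions, a linear Hb rise, confirmation by two consecutive values and no dose reductions. The runs stop at Week 6. Weeks 7 to 16 were not simulated, so the gain from a later window is inferred from the reading at Weeks 4 and 6. Moving the start only to the first dose helps in part, because early on-treatment values are still often below 10.0. The primary endpoint and its power are unaffected. The change is worth making but is not critical to the trial.

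**What to change.** Replace the single endpoint with two proportions, and count pre-treatment values in neither:

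- Hb above 12.0 g/dL, on all values after the first dose to Week 16, so that overshoot during fixed dosing is kept.
- Hb below 10.0 g/dL, on values from the Week 6 visit (start of the dose-adjusted period) to Week 16.

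If placebo is shown alongside, limit that display to values up to Week 10. The SAP can define confirmed.

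The cost is the rewording of one endpoint in the synopsis and Section 5.2. No new sample should be needed: Appendix A of the preceding protocol version schedules a complete blood count at Weeks 6, 10, 14 and 16 (the latest version breaks off before its own schedule). The small downside is that values below 10.0 before Week 6 no longer count here; the mean Hb change at Week 6 already covers that period.

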## 6 STUDY DESIGN

[figure not shown]
### 6.1 Study Design

This is a Phase 2, randomized, double-blind, placebo-controlled, dose-finding study to assess the efficacy, safety, tolerability, PK, and PD of orally administered vadadustat in Japanese subjects with anemia secondary to NDD-CKD.

The study has a planned enrollment of 48 subjects to be enrolled at approximately 25 sites in Japan. There will be 16 subjects in each of the 3 tablet-count groups.

An overview of the study design is presented in Figure 3.

**Figure 3: Overview of Study Design**

The study will include the following periods:

- Eligibility screening period (up to 4 weeks)
- Primary efficacy period (6 weeks; Weeks 1 to 6)
- Dose adjustment and maintenance period (10 weeks) include the following:
  - Blinded dose adjustment and data cleaning period (4 weeks; Weeks 7 to 10): Individual subject data (from screening to Week 6) will be cleaned and locked and individual subject unblinding will take place at the Week 10 visit
  - Open-label extension period (6 weeks; Weeks 11 to 16): Subjects randomized to receive vadadustat treatment during the blinded period will continue into this period
- Safety follow-up period (2 weeks; Weeks 17 and 18): Subjects who complete participation in the open-label extension period and subjects who discontinue early during the blinded study periods will complete the safety follow-up period. Subjects identified as having received placebo during the Week 10 unblinding visit will not participate in this safety follow-up period.

Subjects will participate in a screening period (4 days to 4 weeks) to determine study eligibility, and eligible subjects will be randomized following the screening period.

Using a central randomization system, subjects will be randomized 1:1:1 to receive 1, 2, or 4 tablets at their baseline visit (Day 1). Within each tablet-count group, subjects will be randomized 3:1 to receive vadadustat (150, 300, or 600 mg vadadustat) or placebo. See [Section 8.2.2](#) for information regarding the randomization scheme.

Blinded study drug treatment will be administered during a 6-week primary efficacy period. See [Section 8.2.4](#) for information on study drug administration.

The primary efficacy period includes fixed-dose treatment to establish a dose-response relationship. However, if Hb levels increase too rapidly or if the Hb levels exceed the desired range, the blinded study drug dose can be decreased or discontinued (see [Section 8.2.4](#)).

After completing the primary efficacy period, subjects will continue to a 10-week dose adjustment and maintenance period including a 4-week, blinded dose adjustment and data cleaning period and a 6-week, open-label extension period (see [Sections 8.2.5](#) and [8.2.6](#)). Dose will be adjusted to achieve a target Hb of 10-12 g/dL, and dose adjustments will be based on dose adjustment guidelines (see [Section 8.2.7](#)).

Individual subject's study data (from screening to Week 6) will be cleaned and locked during the 4-week, blinded, dose adjustment period.

At the Week 10 visit, treatment assignment will be unblinded on an individual subject basis. Subjects who were randomized to receive placebo will end study participation after unblinding at the Week 10 visit. Subjects who were randomized to receive 1 of the 3 vadadustat doses will continue receiving vadadustat during the 6-week, open-label extension period.

Vadadustat treatment will stop after the extension period has been completed (Week 16) and subjects will continue in a 2-week follow-up safety period (Week 17-18).

The clinical and safety assessments will be performed as described in [Section 9.3](#) and as listed in [Appendix A](#).

## 6.2 Study Duration

Individual subjects will participate in the study for up to 22 weeks, including the eligibility screening period (up to 4 weeks), primary efficacy period (6 weeks), blinded dose adjustment and data cleaning period (4 weeks), open-label extension period (6 weeks), and safety follow-up period (2 weeks).

Only subjects who are randomized to receive vadadustat will continue in the open-label extension period and the safety follow-up period. Subjects who are randomized to receive placebo during the blinded treatment period will discontinue from the study after unblinding at Week 10.

[figure not shown]
## 6.3 Rationale for Study Design

The study design of this randomized, double-blind, placebo-controlled, dose-finding study in Japanese subjects with anemia secondary to NDD-CKD is modeled on a previously completed dose-finding study in Caucasian subjects with anemia secondary to NDD-CKD (Study AKB-6548-CI-0005).

A treatment duration of 6 weeks will be adequate to demonstrate the dose-response relationship of vadadustat with change in Hb, as 6 weeks of treatment with vadadustat in

Study AKB-6548-CI-0005 was adequate to establish a statistically significant dose-response relationship (as shown in Figure 4). An additional 10-week maintenance period will be conducted to evaluate the effect of dose adjustments and demonstrate the maintenance effect on Hb.

**Figure 4: Absolute Change in Hemoglobin ( $\pm$  Standard Error of Mean, g/dL) at Week 6 Compared to Baseline (Study AKB-6548-CI-0005)**

Note: 25% of the subjects in the 630 mg vadadustat treatment group and 10% of subjects in the 500 mg vadadustat treatment group had their doses reduced by Week 4.

Note: Two tailed paired t-test of hemoglobin: Baseline versus Week 6,  $p < 0.01$

#### 6.4 Dose Justification

The doses to be used in the present study (150, 300, and 600 mg once daily) were previously evaluated in the ethno-bridging study (Study AKB-6548-CI-0020). The results from Study AKB-6548-CI-0020 showed that the doses are safe and well tolerated, and similar PK and PD responses to vadadustat were demonstrated between the Caucasian and Japanese healthy subjects.

Furthermore, the same dose range of 150 mg to 600 mg was previously tested in US-based studies enrolling more than 200 subjects with either NDD-CKD (Phase 2 studies AKB-6548-CI-0005 and AKB-6548-CI-0007) or DD-CKD (Phase 2 study AKB-6548-CI-0011). In these completed studies, the dose range of 150-600 mg was shown to be safe, well-tolerated, and efficacious in raising and/or maintaining Hb at the desired target level in patients with anemia secondary to NDD-CKD or DD-CKD. Importantly, the dose range provides great flexibility in enabling adjustment of vadadustat dose according to an individual patient's Hb response. The product labeling for NESPO® and ESPO® in Japan also allow for adjustable dosing based on Hb response in individual patients.

## 7 SELECTION AND WITHDRAWAL OF SUBJECTS

### 7.1 General Criteria

The study population will consist of male and female Japanese adults aged 20 years or older with anemia secondary to NDD-CKD who are not currently being treated with an ESA.

To be eligible for this study, a subject or their legally acceptable representative must have provided valid informed consent and must meet all of the following criteria. No study procedures (including screening tests) may be performed until after the informed consent has been legally signed.

### 7.2 Inclusion Criteria

Subjects must meet all of the following inclusion criteria to be eligible for study participation:

1. Male and female Japanese subjects, aged 20 years or older
2. Diagnosis of CKD based on an estimated glomerular filtration rate (eGFR) of  $\leq 60$  mL/min/1.73 m^2 (using the 2009 Japanese Society of Nephrology equation; [Matsuo 2009](#))
3. Not currently being treated with dialysis and not expected to start dialysis within 3 months of screening
4. Hemoglobin (Hb)  $\leq 10.5$  g/dL during screening
5. Serum ferritin  $\geq 50$  ng/mL during screening
6. TSAT  $\geq 20\%$  during screening
7. Folate and vitamin B12 greater than or equal to the lower limit of normal during screening
8. Understands the procedures and requirements of the study and provides written informed consent and authorization for protected health information disclosure

